1.0 BACKGROUND AND RATIONALE

Acute myeloid leukemia (AML) remains a difficult-to-treat malignancy, claiming approximately 10,000 lives each year in the U. S. alone [1-4]. Treatment improvements have been very gradual at best over the last two decades, and even with contemporary, intensive treatment regimens, only few patients will be alive 2-5 years after initial diagnosis [5, 6].

The majority of AML patients will require salvage therapy because of the high rates of failure to respond to initial therapy or relapse after standard remission induction therapy. Probably the most commonly used salvage regimen employs high-dose cytarabine (HiDAC). Patients with relapsed/refractory AML have poor outcomes. In patients who have relapsed within 1 year of initial remission or who have primary refractory disease, the complete remission (CR) rate with HiDAC is only about 15% [7]; such patients represent the great majority presenting for salvage therapy. Given these poor results, the need for new therapies in AML is clear.

Rationale for use of hypomethylating agents in AML

Decitabine 20 mg/m2 has been given as a single agent typically in 5-day cycles; CR rates in older newly diagnosed patients are about 25%.[8] Subsequently, several groups experimented with lengthening to 10-day cycles (also at 20 mg/m2 daily). Ritchie et al described with CR rates of 40% for newly diagnosed and 15.7% for relapsed / refractory patients, and other than hematologic / infectious toxicities, AEs were mild with no grade >2 events reported.[9] In fact, the authors even conclude by suggesting that the safety profile of 10 days of decitabine suggests that this could be combined safely with other agents. Blum et al reported on decitabine 20 mg/m2 daily for 10 days in 53 newly diagnosed patients and demonstrated a 47% CR rate; Nonhematologic / infectious grade >2 toxicities were rare, including fatigue (6%), anorexia (2%), mucositis (6%), hypoxia (15%), arrhythmia (6%), rash (4%). The only patients who died within 2 months of treatment were those who had failed to achieve remission (n=7) / had a severe infection (n=1).[10] Similar trends have been seen with non-randomized data for single-agent azacitadine: 7-day courses were associated with non-significantly improved CR rates (16.7% vs. 12.1%) and survival (14.9 vs. 13.2 months), with similar rates of hematologic toxicity and similar rates of requiring dose modification / treatment interruption.[11] While there is some evidence that longer duration of hypomethylating agents may improve efficacy, and while these treatments appear to be safe, remission rates are disappointingly low, suggesting that we should explore more effective treatments for AML. One such option is combining two treatments with limited efficacy (decitabine and chemotherapy) with the hope of finding synergistic efficacy. However, we currently do not know how best to combine these agents. Concurrent dosing may be the most obvious and most efficient method, but there is some pre-clinical evidence suggesting that giving decitabine prior to chemotherapy may improve efficacy.

Over the last several years, new insight into leukemogenesis has led to the exploration of targeting epigenetic mechanisms for treatment of AML. Epigenetic silencing of structurally normal genes by aberrant DNA methylation, mediated by DNA-methyltransferase (DNMT) enzymes, has been shown to contribute to myeloid leukemogenesis by disrupting important cellular pathways such as differentiation, proliferation, and apoptosis [12, 13]. In contrast to structural changes, epigenetic changes can be pharmacologically reversed, resulting in gene re-expression and restoration of normal cellular functions. Decitabine and azacitidine are cytidine analogs that deplete DNA methyltransferases, often referred to as a "hypomethylating cytidine analogs" (HCAs). Pre-clinical studies on the functional effects of HCAs in hematopoietic cell lines demonstrated that decitabine induced a dose-dependent demethylation and apoptotic

response in myeloid leukemia cells [14]. Additionally, Qin *et. al.* found that combinations of decitabine and cytarabine synergistically killed leukemic blasts [15], with exposure to decitabine followed by treatment with cytarabine resulting in a more pronounced synergistic killing effect compared to concomitant use of both agents [14].

Hypomethylating agents prior to intensive chemotherapy: evidence on tolerability

Building on the hypothesize that pretreatment (i.e., priming) with a hypomethylating agent such as decitabine might sensitize resistant leukemic cells to cytotoxic chemotherapeutics and increase the efficacy of induction chemotherapy in AML, a few studies have examined combinations of decitabine priming and cytotoxic chemotherapy for the treatment of patients with AML. A good way to determine whether HMAs add to the toxicity profile of standard AML chemotherapy is in the context of a randomized trial, which are rare in acute leukemia. In this case, however, we can draw from the AML-AZA trial, which randomized patients to 7+3 induction chemotherapy and high-dose cytarabine consolidation with or without 5 days of azaciditine priming before cycles. The difference in AEs was not significant, and early death rates did not differ (6% vs. 5%).[16] Several trials have used decitabine priming prior to intensive chemotherapy using a dose escalation strategy starting at 20 mg/m² for 5 days, and none has been able to identify an MTD. Scandura et al used decitabine priming for 7+3 chemotherapy with decitabine escalated from 5 to 7 days. Duration of neutropenia and incidence of infection were similar. There was more GI toxicity and mucositis at higher doses, but all toxicities were grade 3 or lower and would not have limited dose escalation had the protocol been written to allow for this.[17] More recently, we have submitted to ASH the final results of our phase 1/2 study of decitabine-primed mitoxantrone, etoposide, and cytarabine (MEC), which uses 1g/m² of Ara-C daily for 6 days and safely administered decitabine for 10 days. Earlier results from this protocol, FH #2652, were included in our prior submission. Updated results with 52 patients with relapsed / refractory AML showed that grade >2 non-hematolgoic / noninfectious toxicities were fatigue, nausea, and mucositis. Among 9 deaths on the study, 5 were related to infection, 1 to disease, 2 to respiratory failure, and 1 to hemorrhage. We have also analyzed unpublished data on patients treated off protocol with this regimen, and in total 71 patients have received decitabine-primed MEC between 2013 and 2015. Many patients treated off protocol were given decitabine prior to MEC without the standard 5 day rest period between decitabine and chemotherapy, and there was no difference in treatment efficacy or survival among these patients vs. those who had the 5 day break, indicating that the pre-clinical models suggesting better efficacy with optimal priming may not transplant perfectly into the clinic. In fact, it is possible that the benefits of hypomethylating agents do not actually require priming. and that they could be seen with concurrent administration.

Hypomethylating agents concurrent with intensive chemotherapy: evidence on tolerability

It remains unknown whether priming is indeed the optimal way of combining decitabine with intensive chemotherapy, or whether similar results could be achieved with concurrent administration of decitabine along with chemotherapy. Decitabine at 25-30 mg/m² for 4 days has been combined with intermediate doses of ara-C without increase in severe infection rate or early mortality over decitabine alone in MDS (NCT01674985).[18] Our institution has been giving decitabine 20mg/m² for 10 days concurrent with high-dose cytarabine as part of protocol FH #9109 since 2014. While induction uses intermediate doses of cytarabine, patients who fail to achieve remission with this induction are then given 10 days of decitabine concurrent with high-

.

Protocol 9713.00

dose cytarabine $(1g/m^2 \text{ daily for 5 days})$. Per their protocol, "Although ara-C has yet to be combined with 10 days of decitabine the absence of toxicity with tosedostat plus... higher doses of ara-C $(1g/m^2)$ suggests excess toxicity will not be an issue..." This protocol was approved for use in older patients at high risk for treatment-related mortality (TRM scores >13.1), compared to those required for this present study (<9.2). Despite the high-risk patient population in 9109, this combination has been well-tolerated, with unpublished results communicated by the study PI showing that only 4 of 12 patients had a *temporary* grade 3-4 non-infectious / non-hematologic adverse event related to treatment (muscle weakness in 2, fatigue in 1, and hyperbilirubinemia in 1).

Rationale for studying concurrent decitabine rather than primed decitabine

While it remains unknown whether priming is the optimal way of combining decitabine with intensive chemotherapy, we found that having a randomized study of concurrent vs. primed decitabine with GCLAM was impractical from an enrollment standpoint. After an initial 10 months of having this study open as a randomized study with low accrual, we found that the major barrier to enrollment was the randomization component. Specifically, patients did not want to be randomized to the sequential arm because this would entail an additional 15 days of treatment. For patients receiving treatment at our center who were lodged away from home. having an extra 15 days in Seattle was considered overly onerous, and therefore patients chose to enroll in different protocols or receive treatment off protocol rather than being randomized on protocol 9713. We did not note any clear difference in toxicity or efficacy between study arms at that point, and so we opted to shut down the sequential arm and enroll on the concurrent arm alone. This is consistent with unpublished data from our institution on 71 patients treated with decitabine-primed MEC both on and off protocol between 11/15/12 and 11/15/16 showing that there is no difference in CR rates or survival outcomes between patients who had a 5-day chemofree interval after decitabine priming versus those who received MEC immediately following the last dose of decitabine, and so it may be that pre-clinical models of priming effects do not translate perfectly in vivo. It is possible that any benefits of hypomethylating agents like decitabine do not require priming, and that these benefits could be achieved with concurrent administration of decitabine and chemotherapy.

Rationale for combining decitabine with G-CLAM/Demonstration of safety and tolerability of using escalated doses of mitoxantrone as part of G-CLAM

In 2008, Polish investigators reported their experience with the use of G-CSF, cladribine (5 mg/m² on days 1-5), high-dose cytarabine (2,000 mg/m² on days 1-5), and mitoxantrone (10 mg/m² on days 1-3; "G-CLAM") for the treatment of primary refractory AML or early relapsed disease, with encouraging activity – among 118 treated patients, a complete remission (CR) rate of 58% was obtained – and acceptable tolerability with low rates of grade >2 non-infectious / non-hematologic AEs, the most common ones being nausea (20%), diarrhea (14%), mucositis (10%), and bleeding (10%) [19]. Starting in 2014, we have conducted a phase 1/2 study of dose-escalated G-CLAM in adults with newly diagnosed or relapsed/refractory AML or high-risk MDS (NCT02044796, Fred Hutch #2734.00). Preliminary results from the phase 1 portion of this study were presented in abstract form at the American Society of Hematology in 2015: 18 mg/m²/day was identified as the MTD of mitoxantrone in newly diagnosed patients, and 16 mg/m²/day in relapsed/refractory patients. Among 31 newly diagnosed patients with median age 58 (range: 27-77) years, median TRM score 2.83 (range: 0.15-5.54), 1 patient died within 28

days of treatment initiation from thrombocytopenia-related intracranial hemorrhage. Overall, 29/31 patients (93.5%) achieved a CR, including 24 (77.4%) with complete count recovery, with 1-2 cycles of chemotherapy. One DLT occurred at each of dose levels 3 and 4 (respiratory failure in both cases), establishing 18 mg/m²/day as the MTD of mitoxantrone. Besides infections and neutropenic fever, maculopapular rash, nausea, and hypoxia were the most common grade 3+ adverse events. There were 26 relapsed and refractory patients treated in Phase 1 with median age 57 (37-77) years, median TRM score of 1.73 (range: 0.29-3.92). 2 patients died within 28 days of treatment initiation from sepsis and cardiogenic shock respectively. Overall, 13/36 patients (50%) achieved a CR, including 8 (31%) with complete count recovery. One DLT occurred at dose level 1 (nausea) and 2 at dose level 4 (encephalitis and cardiogenic shock), establishing 16 mg/m²/day as the MTD of mitoxantrone. Besides infections and neutropenic fever, the most common grade 3+ adverse events were nausea, hypoxia (fluid overload and infection related), and maculopapular rash.[20] The final results from the phase 1/2 study in newly-diagnosed patients were submitted in abstract form to ASH this year; similar rates of response and adverse events were reported.

PROTOCOL UPDATE (2-2018)

Rationale for restricting enrollment to newly diagnosed (ND) patients

Analysis of treatment outcomes for relapsed/refractory (RR) patients enrolled in this protocol revealed an increased rate of delayed blood count recovery (MLFS) over what would be expected based on experience with GCLAM without decitabine. Based on these cases, revisions to the RR arm of this protocol are being discussed. These revisions are beyond the scope of what can be accomplished with a protocol modification, and so we have elected to restrict this protocol to ND patients and to work on a new protocol for RR patients.

Rationale for allowing only 1 cycle of decitabine + GCLAM

This protocol initially called for multiple cycles of decitabine in combination with chemotherapy: patients who failed to achieve CR without measurable residual disease (MRD), or MRDneg CR, were eligible for a 2nd cycle of decitabine + GCLAM, while those who did achieve this outcome were eligible for consolidation with decitabine + GCLA. Review of outcomes from the 4 ND patients who received on-protocol consolidation showed that 2 had delayed or absent recovery of neutrophils and platelets not related to leukemia, or morphological leukemia-free state (MLFS). Although it is difficult to interpret results from so few patients, in light of results from RR patients showing higher rates of MLFS than we would normally expect, we opt to restrict patients to a single cycle of decitabine in combination with GCLAM. Patients achieving MRDneg CR have the option of receiving GCLA consolidation (which is a standard therapy that they could receive on or off protocol), while those who do not achieve MRDneg CR will be taken off study. Because we recognize MLFS as a concern with this regimen, we will add criteria to the stopping rules to include bone marrow aplasia.

Rationale for adding a Phase 2 expansion cohort

Based on the 6 ND patients who have had their responses assessed, the combination of decitabine for 10 days and GCLAM appears to be effective. Within our first cohort of 6 patients, we had 1 DLT (a patient experienced early death), but responses in the other 5 patients showed MRDneg CR. Without an expansion cohort, we only have room to enroll another 4 patients on

Protocol 9713.00

the trial to determine the MTD or recommended Phase 2 dose (RP2D) assuming that the remaining patients have only 0 or 1 DLT. Because of these promising early results, we plan to expand our study in ND patients at the MTD/RP2D. The Phase 2 expansion includes stopping rules for both efficacy and safety.

2.0 **OBJECTIVES**

2.1 Primary Objective

- **2.1.1** Estimate the maximum tolerated dose (MTD) of decitabine when used concomitantly with G-CLAM in patients with newly diagnosed AML and highrisk MDS.
- **2.1.2** Compare, within the limits of a phase 1/2 study, the rate of complete remission without measurable residual disease (MRDneg CR) with decitabine + G-CLAM at the MTD compared to similar patients treated previously with G-CLAM alone.

2.2 Secondary Objectives

- 2.2.1 Evaluate, within the limits of a phase 1/2 study, disease response (complete remission, overall response rate) relapse-free survival (RFS), event-free survival (EFS), and overall survival (OS) in patients with newly-diagnosed AML / high-risk MDS.
- **2.2.2** Describe, within the limits of a phase 1/2 study, the toxicity profile of the study regimen.

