6.0 TREATMENT PLAN

This study is a single-center, open-label phase 1/2 study of decitabine given concomitantly with G-CLAM chemotherapy in adults with newly diagnosed AML or high-risk MDS. Since prior studies have suggested that the hypomethylating activity of decitabine plateaus at 20 mg/m²/d [23] and since data from Fred Hutch #2652.00 discussed above show that decitabine can be given safely for 10 days prior to intensive chemotherapy, we will start our trial with 10 days of decitabine at 20 mg/m²/d and will de-escalate the dose based on DLTs. We will use G-CLAM dose established based on data from Fred Hutch #2734.00 described above. Bone marrows will be reassessed upon blood count recovery or between day Days +25 to +35 after start of G-CLAM chemotherapy, whichever occurs first. Patients achieving CR or CR with incomplete neutrophil or platelet count recovery (CRi) after one induction course are eligible for consolidation chemotherapy with G-CSF, cladribine, and cytarabine ("G-CLA"), which should begin within 6 weeks of achieving CR/CRi once patients have recovered to \leq Grade 2 toxicities from the previous course of therapy.

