6.6 Assessment for Response after First Induction Course

A bone marrow aspirate should be obtained upon blood count recovery (i.e. ANC >1,000/ μ L and platelet count >100,000/ μ L) or between Days +25 to +35 after start of G-CLAM chemotherapy, whichever occurs first; a bone marrow biopsy should be obtained if spicules are absent from the aspirate sample. In patients with unclear response status, the bone marrow examination should be repeated every 7-10 days until the response can be assessed or until Day +45.

- **6.6.1** Patients achieving MRDneg CR: Patients are eligible for consolidation chemotherapy, as described in section 6.8.
- **6.6.2** Patients achieving CR with MRD, CRi, or those with persistent disease: patients are eligible for a second course of induction chemotherapy consisting of G-CLAM without decitabine provided all non-hematologic toxicities have resolved

to Grade <2. For patients who experienced \geq Grade 3 non-hematologic / noninfectious toxicity during the first induction, a dose reduction is recommended as described in section 6.7. Patients who achieve CR or CRi after a second induction are eligible to receive consolidation chemotherapy, as described in section 6.8.

6.6.3 Patients with persistent aplasia without evidence of disease after Day +45: patients will be removed from protocol.

6.7 Dose Modifications of Chemotherapeutic Drugs for Initial and Subsequent Treatment Cycles

The following dose modifications are suggested both for induction cycle #1 (i.e. if organ function parameters worsen between baseline and start of chemotherapy) and subsequent treatment cycles:

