- 6.7.1 If a patient develops Grade ≥ 3 non-hematologic toxicity other than Grade 3 infections within 21 days from the last dose of G-CLAM, subsequent doses of cladribine and cytarabine will be reduced by 25% and the dose of mitoxantrone will drop by 2 mg/m². The patient may receive future cycles using this dosereduced regimen, if the patient demonstrated potential response and once the nonhematologic toxicity has resolved to a level of < Grade 2. If a patient develops Grade \geq 3 non-hematologic toxicity other than Grade 3 infection within 21 days from the last dose of the first dose-reduced regimen, the dose of the cladribine and cytarabine for subsequent cycles will be reduced by 50%. Mitoxantrone will only be given for 1st and 2nd induction and is not part of post-remission chemotherapy. and so further dose reductions will not be required. The patient may receive future cycles using the new dose-reduced regimen, if the patient demonstrated potential response and once the non-hematologic toxicity has resolved to a level of < Grade 2, unless, at any time, a patient displays Grade ≥ 3 non-hematologic toxicity other than Grade 3 infections while receiving the 50% dose-reduced regimen, at which point the patient will not be eligible for additional therapy as part of the protocol. Furthermore, if patients require treatment interruption of > 21days from the planned start of the next cycle, the patient will be not be eligible for additional therapy as part of the protocol.
- 6.7.2 Mitoxantrone: Consider dose reduction of mitoxantrone by 50% if the bilirubin concentration is $1.5-4.5 \times IULN$. The dose of mitoxantrone will be reduced to 25% if the bilirubin concentration is >4.5 x IULN.
- 6.7.3 Cladribine: If the serum creatinine exceeds 2.0 mg/dL and/or estimated creatinine clearance (calculated by Cockcroft-Gault) decreases to less than 50 mL/min during therapy, we will consider dose reduction in discussion with the Oncology Pharmacist.
- **6.7.4** Cytarabine: If the serum creatinine exceeds 2.0 mg/dL and/or estimated creatinine clearance (calculated by Cockcroft-Gault) decreases to less than 50 mL/min during therapy, we will consider dose reduction in discussion with the Oncology Pharmacist.

6.8 Consolidation Therapy

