After a achieving MRDneg CR after 1 cycle of decitabine + G-CLAM or after achieving CR/CRi after 1 cycle of decitabine + G-CLAM followed by GCLAM without decitabine, patients are eligible for consolidation therapy with G-CLA. Consolidation will not include decitabine.

- **6.8.1** The treatment is identical to the induction course but without decitabine or mitoxantrone (i.e. G-CSF, cladribine, and cytarabine, "G-CLA"), provided the patient had <Grade 3-4 non-hematologic / non-infectious toxicity during induction. If there was such toxicity, doses should be reduced as described in section 6.7.
- **6.82** Consolidation courses should start within 6 weeks of response assessment once patients have recovered to Grade ≤ 2 toxicities from the previous course of therapy.
- **6.8.3** Patients can receive up to 4 courses of consolidation therapy.
- **6.8.4** Patients can proceed to transplantation barring contraindications and if a suitable donor is available.

6.9 Supportive Therapy

- **6.9.1** All patients will be adequately hydrated and receive appropriate anti-emetics based upon NCCN guidelines [24].
- **6.9.1** Growth factors may be used according to institutional practice guidelines or the preference of the attending physician.
- **6.9.2** Antimicrobial prophylaxis should be used according to institutional practice guidelines. In case of neutropenic fever, standard diagnostic testing will be performed, and empiric antibiotic coverage will be utilized as per usual care and standard institutional practices (SCCA, UWMC, and Fred Hutch).
- **6.9.3** Transfusional support should be carried out according to institutional practice guidelines.

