The endpoints of the phase 1 portion of this study are the determination of the MTD of decitabine in newly-diagnosed patients. Provided that the MTD is successfully determined, enrollment in the phase 2 portion of this trial at the MTD will be conducted in this population. The endpoints for the phase 2 portion of this study are (primary) MRDneg CR compared to historical controls of G-CLAM alone and (secondary) disease responses, relapse-free, and overall survival. For the primary outcome comparison, response rates will use the best response after up to 2 cycles of induction (1 with decitabine G-CLAM and 1 with G-CLAM alone).

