11.0 GUIDELINES FOR SERIOUS ADVERSE EVENT REPORTING

11.1 Expedited Reporting Requirements and Reporting Period

In accordance with Fred Hutch/UW Cancer Consortium IRB policy, all adverse events (AEs; whether occurring on-site or off-site), which in the opinion of the principal investigator are (1) unexpected, and (2) related or possibly related to the research, and (3) serious or suggests that the research places research participants or others at a greater risk of physical or psychological harm than was previously known or recognized, will be submitted to the IRB within ten (10) calendar days of learning of the problem. Both the "Expedited Reporting Form for Unanticipated Problems or Noncompliance" and the "Adverse Event Reporting Form", or equivalent forms, will be completed for this reporting. AEs will be monitored from the time of initial drug delivery. Upon completion of induction chemotherapy (1-2 cycles), patients will be monitored for late toxicities for 1 month or until additional anti-AML therapy is given off of this protocol.

11.2 Definitions: according to ICH guidelines and 21 CFR 312.32, IND Safety Reports, and ICH E2A,Definitions and Standards for Expedited Reporting, and adverse event is defined as follows:

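### Section 6.0 and the section 1 rationale give rules for patients not in MRDneg CR after cycle 1 that conflict with 6.6 to 6.8 and with the two-induction primary endpoint (minor)

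*Combined protocol and SAP*

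**What the plan says.** **Section 1, rationale for a single cycle of decitabine + GCLAM.** Patients in MRDneg CR may have GCLA consolidation, "while those who do not achieve MRDneg CR will be taken off study".

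**Section 6.0, Treatment Plan.** "Patients achieving CR or CR with incomplete neutrophil or platelet count recovery (CRi) after one induction course are eligible for consolidation chemotherapy" with G-CLA. MRD status is not mentioned.

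**Section 6.6.1**, for patients in MRDneg CR after the first induction: "Patients are eligible for consolidation chemotherapy, as described in section 6.8".

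**Section 6.6.2**, for CR with MRD, CRi or persistent disease: "patients are eligible for a second course of induction chemotherapy consisting of G-CLAM without decitabine provided all non-hematologic toxicities have resolved" to below Grade 2.

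**Section 6.6.3** removes patients whose aplasia persists past Day +45 with no leukemia found.

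**Section 6.7.1**: "Mitoxantrone will only be given for 1st and 2nd induction and is not part of post-remission chemotherapy".

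**Section 6.8** opens consolidation to MRDneg CR after one cycle, or "after achieving CR/CRi after 1 cycle of decitabine + G-CLAM followed by GCLAM without decitabine, patients are eligible for consolidation therapy with G-CLA".

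**Section 6.12.3** makes failure to reach CR or CRi a reason for removal only once the allowance of two inductions is used.

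**Section 8.5**, for the primary comparison: "response rates will use the best response after up to 2 cycles of induction (1 with decitabine G-CLAM and 1 with G-CLAM alone". Section 14.3 uses the same window.

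**Section 11.1**: "Upon completion of induction chemotherapy (1-2 cycles), patients will be monitored for late toxicities for 1 month".

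**The concern.** A patient in CR with MRD, or in CRi, after cycle 1 has three possible paths, depending on which sentence is followed: off study (section 1), straight to G-CLA, which contains no mitoxantrone (section 6.0), or re-induction with G-CLAM (6.6.2). A patient with persistent disease has two: off study, or re-induction.

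This bears on the primary endpoint because MRDneg CR is scored as best response over up to two inductions. A patient removed under section 1, or consolidated under 6.0 while MRD-positive or in CRi, would probably be scored as a non-responder without having had the second induction that the endpoint allows. It is also a matter of patient care, since the sentences differ on how residual leukemia is handled.

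**Working it through.** **1. The rules side by side, by status after cycle 1**

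| Status after cycle 1 | Section 1 rationale | Section 6.0 | Sections 6.6 to 6.8 |
|---|---|---|---|
| MRDneg CR | G-CLA optional | G-CLA | G-CLA |
| CR with MRD | off study | G-CLA | second induction, G-CLAM alone |
| CRi | off study | G-CLA | second induction, G-CLAM alone |
| Persistent disease | off study | silent | second induction, G-CLAM alone |
| Aplasia past Day +45, no leukemia | off study | silent | off protocol |

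The first and last rows show no conflict. The second and third conflict three ways, the fourth two ways. Section 6.0 does not forbid re-induction. Its fault is a looser entry to consolidation than 6.6.1 and 6.8 allow.

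**2. Which text is the outlier.** Sections 6.6.2, 6.7.1, 6.8, 6.12.3, 8.5, 11.1 and 14.3 all presuppose a second induction. Only the section 1 sentence excludes it. On consolidation, 6.6.1 and 6.8 agree and 6.0 stands alone.

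**3. Is the section 1 sentence superseded?** The paragraph opens with the old plan of repeated decitabine cycles. The quoted sentence comes after the decision to restrict decitabine to one cycle and states the rule from then on. It is dated rationale, but it is not a description of the old plan.

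**4. The plan's design figures.** Inputs from 14.3: null rate 0.65, alternative 0.80, continue if at least 13 of 19 respond, success if at least 31 of 41 respond. Exact calculation:

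P(success | p) = Σ over x = 13 to 19 of P(Bin(19, p) = x) × P(Bin(22, p) ≥ 31 − x)

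- p = 0.65: 0.0960, against a stated type I error of 10%.
- p = 0.80: 0.8002, against a stated power of 80%.
- Early stopping under the null, P(Bin(19, 0.65) ≤ 12): 0.519, against a stated 51%.

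The design reproduces and is not in question.

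**5. Direction of any effect.** For patient i, let Y_i = 1 if MRDneg CR is reached when the second induction is available as in 6.6.2, and Y'_i the same when it is withheld. A best response over two inductions cannot be worse than the response after one, so Y'_i ≤ Y_i. Section 8.5 counts induction cycles, so a conversion during consolidation is taken not to count. Both decision rules require a count at or above a cut-off, so a trial that succeeds on the Y' counts would also succeed on the Y counts. Withholding the second induction can therefore only lower the probability of success. At a true rate of 0.65 that probability stays at or below 0.0960.

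**6. Size.** A figure would need the share of eligible patients who convert to MRDneg CR in the second induction and the share handled under section 1 or 6.0 instead of 6.6.2. The documents give neither.

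**The case against.** The strongest reply is that nobody would be misled. The section 1 sentence sits in the Background under a dated protocol update and explains an amendment. The documents do not show when 6.6.2 took its present wording. Section 6.12, which governs removal from treatment, contemplates two inductions. Section 6.0 is an overview whose wording is permissive, with 6.6 and 6.8 supplying the detailed rule. The study is single-center, and one principal investigator oversees treatment of all subjects. The second induction is optional and depends on toxicity resolving, so some patients would stop after one cycle under any wording, and an endpoint over up to two cycles accommodates that. Of the six assessed newly diagnosed patients described in section 1, five reached MRDneg CR and one died early; none fell in a category where the texts conflict, although they were treated under the earlier plan.

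Most of this stands, and it is why the point is minor. It does not remove the conflict: 6.0 is current treatment-plan text, and it contradicts 6.6.1 and 6.8 on the handling of residual disease.

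A reader might go further and infer a definite loss of power, or try to bound the number affected by the expected number of patients not in MRDneg CR after cycle 1. The documents support neither. Any power figure would rest on an assumed conversion or misrouting rate. The count of all patients not in MRDneg CR includes early deaths and persistent aplasia, where the rules do not conflict, so it does not bound the affected subgroup, which could be close to zero.

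**Conclusion.** Wrong as written, of minor severity. Two sentences, one in 6.0 and one in the section 1 rationale, do not match the detailed rules, which agree with each other and with the primary endpoint. Following either sentence could cost a patient the second induction that the endpoint counts. The bias would be toward a lower observed MRDneg CR rate and a lower chance of declaring success, with no inflation of type I error. That direction rests on reading 8.5 as counting induction responses only. The size cannot be derived.

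The documents do not support a reading that the endpoint is undefined, since 8.5 and 14.3 state it consistently. Nor do they show that any patient was diverted.

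**What to change.** - **Section 6.0:** state that G-CLA consolidation is open only to patients in MRDneg CR after one course, or in CR or CRi after a second induction.
- **Section 1 rationale:** replace the sentence with one saying that patients not in MRDneg CR after cycle 1 receive no further decitabine; that those with CR with MRD, CRi or persistent disease may have a second induction with G-CLAM alone under 6.6.2; and that those with aplasia persisting beyond Day +45 and no sign of leukemia leave the protocol under 6.6.3.

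The cost is a wording amendment to two sentences. It needs no additional patients or procedures, and the Simon design (19 then 41 patients, cut-offs 13 and 31) stays as it is.
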